3. INTRODUCTION

As per ICH E9 (1) the purpose of this document is to provide a more technical and detailed elaboration of the principal features of the analysis described in the protocol, and to include detailed procedures for executing the statistical analysis of the primary and secondary variables and other data.

This Trial statistical analysis plan (TSAP) assumes familiarity with the Clinical Trial Protocol (CTP), including Protocol Amendments. In particular, the TSAP is based on the planned analysis specification as written in CTP Section 7 “Statistical Methods and Determination of Sample Size”. Therefore, TSAP readers may consult the CTP for more background information on the study, e.g., on study objectives, study design and population, treatments, definition of measurements and variables, planning of sample size, randomisation.

Study data (including data entered in the RAVE EDC system and external data provided by suppliers) will be stored in a Clinical Data Repository (CDR).

[figure not shown]
Pharmacokinetic (PK) parameters will be calculated using Phoenix WinNonlin™ software (version 6.3 or higher, [REDACTED]).

The statistical analyses will be performed within the validated working environment CARE, including SAS™ (current Version 9.4, by [REDACTED]), and a number of SAS™-based tools (e.g., macros for the analyses of AE data or laboratory data; Report Appendix Generator system (RAGe) for compilation/formatting of the CTR appendices).

4. CHANGES IN THE PLANNED ANALYSIS OF THE STUDY

All analyses as planned in the CTP will be performed and are described in more detail in this TSAP. The following change compared to the protocol will be made:

In CTP section 7.3 the following was defined: *Important protocol deviation (iPD) categories will be specified in the Integrated Quality and Risk Management (IQRM) Plan, iPDs will be identified no later than in the Report Planning Meeting, and the iPD categories will be updated as needed.* Due to SOP changes, the IPD categories are no longer available in IQRM plan but included in an Excel spreadsheet ([3](#)). The IPD categories originally defined in IQRM plan were transferred to the IPD specification file. Minor changes regarding the IPD categories were performed only.

5. ENDPOINTS

5.1 PRIMARY ENDPOINTS

Section 2.1.2 of the CTP:

The primary endpoint for assessment of safety and tolerability of BI 474121 is the percentage of subjects with drug-related adverse events (SRD part).

The following pharmacokinetic parameters will be determined if feasible (BA part):

- *AUC_{0-t_z} (area under the concentration-time curve of the analyte in plasma over the time interval from 0 to the last quantifiable data point)*
- *C_{max} (maximum measured concentration of the analyte in plasma)*

5.2 SECONDARY ENDPOINTS

5.2.1 Key secondary endpoints

This section is not applicable as no key secondary endpoints have been defined in the CTP.

5.2.2 Secondary endpoints

Section 2.1.3 of the CTP:

[figure not shown]
The following pharmacokinetic parameters will be determined if feasible:

[figure not shown]
SRD part:

[figure not shown]
- *AUC_{0-t_z} (area under the concentration-time curve of the analyte in plasma over the time interval from 0 to the last quantifiable data point)*
- *C_{max} (maximum measured concentration of the analyte in plasma)*

BA part:

- *AUC_{0-∞} (area under the concentration-time curve of the analyte in plasma over the time interval from 0 extrapolated to infinity)*

6. GENERAL ANALYSIS DEFINITIONS

6.1 TREATMENTS

For basic study information on investigational products, assignment of treatment, please see CTP, Sections 3 and 4.

The SRD part is designed as single-blind within dose groups, randomised, and placebo-controlled within parallel dose groups. It is planned to include 56 healthy male subjects in this part of the trial. The subjects will be assigned to 7 groups consisting of 8 subjects per group (6 subjects will receive BI 474121 and 2 will receive placebo).

The BA part will be performed as randomised, open-label, three-way, six-sequence, crossover trial in healthy male subjects. It is planned to include 12 healthy male subjects. The subjects will be randomly allocated to the 6 treatment sequences. There will be a wash out period of at least 7 days between the treatments.

For details see Table 6.1:1 and [Table 6.1:2](#) below.

Table 6.1: 1 Treatments and labels used in the analysis – SRD part

Treatment	Label in dataset	Short label
P*	Placebo, solution, po, qd	Plc os
Q*	Placebo, tablet, qd	Plc tab
A	BI 474121, 0.5 mg/mL solution, 0.25 mg, po, qd	BI 0.25mg os
B	BI 474121, 0.5 mg/mL solution, 1.0 mg, po, qd	BI 1mg os
C	BI 474121, tablet, 2.5 mg, po, qd	BI 2.5mg tab
D	BI 474121, tablet, 2*2.5 mg, po, qd	BI 5mg tab
E	BI 474121, tablet, 10 mg, po, qd	BI 10mg tab
F	BI 474121, tablet, 2*10 mg, po, qd	BI 20mg tab
G	BI 474121, tablet, 4*10 mg, po, qd	BI 40mg tab

*: Each placebo group in the safety evaluation will consist of all placebo treated patients in SRD part, regardless of the dose group in which they were treated.

Table 6.1: 2 Treatments and labels used in the analysis – BA part

Treatment sequence	Short label in dataset	Short label
UVW	BI 474121 10 mg solution / tablet fasted / tablet fed	R/T2/T1
UWV	BI 474121 10 mg solution / tablet fed / tablet fasted	R/T1/T2
VUW	BI 474121 10 mg tablet fasted / solution / tablet fed	T2/R/T1
VWU	BI 474121 10 mg tablet fasted / tablet fed / solution	T2/T1/R
WUV	BI 474121 10 mg tablet fed / solution / tablet fasted	T1/R/T2
WVU	BI 474121 10 mg tablet fed / tablet fasted / solution	T1/T2/R

U=R (Reference treatment)

V=T2 (Test treatment 2)

W=T1 (Test treatment 1)

The short label will be used whenever tables/listings are displayed by treatment sequence. If actual treatment is shown the following labels will be used: BI 10mg tab fed, BI 10mg tab fasted, BI 10mg solution (e.g. AE tables).

Section 1.2.6 of CTP:

The Residual Effect Period (REP) of BI 474121, when measurable drug levels and/or pharmacodynamic effects are still likely to be present, is not known for this first-in-human trial. Conservatively, a minimum observation period of at least 5-fold estimated $t_{1/2}$ has been selected, and thus a REP of 7 days is assumed, i.e. the individual subjects end of trial is on Day 8-15 following dosing with investigational drug at the earliest.

SRD part:

The following study phases will be defined for the analysis of adverse events (AEs):

- **Screening** (ranging from 0:00 h on day of informed consent until first administration of study medication)
- **On treatment** (BI/Placebo treatment ranging from the first time of administration of study medication until 168 hours (7 days) after the last time of administration of study medication)
- **Follow-up (F/U)** (ranging from 168 hours (7 days) after last administration of study medication until 0:00 h on day after trial termination date)

BA part:

The following study phases will be defined for the analysis of adverse events (AEs):

- **Screening** (ranging from 0:00 h on day of informed consent until first administration of study medication)
- **On treatment (BI 10mg tab fed / BI 10mg tab fasted / BI 10mg solution)** (ranging from the first time of administration of study medication until 168 hours (7 days) after

the last time of administration of study medication or until time of next drug administration (whatever occurs first)

- **Follow-up (F/U BI 10mg tab fed / F/U BI 10mg tab fasted / F/U BI 10mg solution)** (ranging from 168 hours (7 days) after last administration of study medication until 0:00 h on day after trial termination date)

Section 7.3.4 of the CTP: *Note that AEs occurring after the last per protocol contact but entered before final database lock will be reported to Pharmacovigilance only and will not be captured in the trial database.*

Displays of AEs will be stratified by dose group as specified in [table 6.1:1](#) and [table 6.1:2](#). The following AE displays will be provided in the report:

Section 15.3 of the CTR displays:

In these displays, the on-treatment phase will be analysed (labelled with the name of the study treatment (short label in SRD part)). Screening and Follow up phases will not be included in this analysis.

The following totals will be provided in addition:

- a total over all Placebo treated on-treatment phases (“**Plc Total**”) – *SRD part only*
- a total over all BI treated on-treatment phases (“**BI Total - tab**”) – *SRD part only*
- a total over all BI treated on-treatment phases (“**BI Total - os**”) – *SRD part only*
- a total over all BI treated on-treatment phases (“**BI Total**”) – *SRD part only*
- a total over all on treatment phases included in this analysis (“**Total**”)

In Appendix 16.1.13.1.8 (for ClinicalTrials.gov and EudraCT only) of the CTR, SRD part and BA part will be combined:

In these displays, the on treatment phase will be analysed (labelled with the name of the study treatment (short label)). Screening and Follow up phases will not be included in this analysis. The following totals will be provided in addition:

- a total over all Placebo treated on treatment phases in SRD part (“**Plc Total – SRD part**”)
- a total over all BI treated on treatment phases in SRD part (“**BI Total – SRD part**”)
- a total over all on treatment phases in SRD part included in this analysis (“**Total – SRD part**”)
- a total over all on treatment phases in BA part included in this analysis (“**Total – BA part**”)
- a total over all BI treated on treatment phases (“**BI Total**”)
- a total over all on treatment phases included in this analysis (“**Total**”)

In Section 15.4 and Appendix 16.2 (Listings) of the CTR displays, screening and follow-up periods will be included and no totals will be provided.

For detailed information on the handling of the treatments refer to Technical TSAP ADS (analysis data set) plan and Analysis Data Reviewers guide.

6.2 IMPORTANT PROTOCOL DEVIATIONS

Data discrepancies and deviations from the CTP will be identified for all treated subjects. Consistency check listings (for identification of deviations of time windows) and a list of protocol deviations (e.g. deviations in drug administration, in blood sampling times, etc.) will be provided to be discussed at the Report Planning Meeting (RPM). At this meeting, all manual deviations identified at the sites by the CRAs and deviations too complex to program will be reviewed by the trial team to decide which are considered important. For definition of important protocol deviations (iPD), and for the process of identification of these, refer to the Boehringer Ingelheim (BI) SOP "Identify and Manage Important Protocol Deviations (iPD)" ([2](#)).

Categories which are considered to be iPDs in this trial were defined in the integrated quality and risk management plan (IQRMP) prior to trial initiation. The iPD list was transferred into the iPD specification file (due to changes in the SOP) ([3](#)). Within this transfer some minor adaptations were done to comply with new naming conventions and categorisations. IPDs will be identified no later than in the Report Planning Meeting and the iPD categories in the iPD specification file will be updated as needed. If any iPDs are identified, they are to be summarised into categories and will be captured in the RPM/DBLM minutes (the decision log) and in the iPD specification file. The decision on exclusion of subjects from analysis sets will be made after discussion of exceptional cases and implications for analyses.

The iPD specification file (e.g. the DV domain specifications) will be stored within the TMF in EDMS.

The iPDs will be summarised and listed.

6.3 SUBJECT SETS ANALYSED

Section 7.3 of the CTP:

For both parts, statistical analyses will be based on the following analysis sets:

- *Treated set (TS): The treated set includes all subjects who were randomised and treated with at least one dose of study drug. The treatment assignment will be determined based on the first treatment the subjects received. The treated set will be used for safety analyses.*
- *Pharmacokinetic parameter analysis set (PKS): This set includes all subjects in the treated set (TS) who provide at least one primary or secondary PK endpoint that was not excluded due to a protocol deviation relevant to the evaluation of PK or due to PK non-evaluability (as specified in the following subsection ‘Pharmacokinetics’). Thus, a subject will be included in the PKS, even if he contributes only one PK parameter value for one period to the statistical assessment. Descriptive and model based analyses of PK parameters will be based on the PKS.*

All ECG analyses are performed on the TS, except for the exposure-response analyses, which are performed on the ECGPCS defined below.

- *ECG Pharmacokinetic Concentration Set (ECGPCS): This subject set includes all subjects from the TS of the SRD part who provide at least one pair of a valid drug plasma concentration and a corresponding (i.e. time-matched) ECG endpoint to be used in the exposure-response analyses. For placebo subjects, the plasma concentration is set to zero and hence always considered as valid. The decision whether a time deviation between PK blood sampling and ECG recording is acceptable (and thus whether the pair of values will be used) is to be made no later than at the RPM before data base lock. For subjects treated with active drug, the decision about concentration value validity needs to be made within the Clinical Pharmacology Group.*

Pharmacokinetics

The pharmacokinetic parameters for drug BI 474121 listed in TSAP [Section 5](#) will be calculated according to BI standard (see BI-KMED-TMCP-MAN-0014 (6)).

Plasma and urine (in the SRD part of the trial) concentration data and parameters of a subject will be included in the statistical pharmacokinetic (PK) analyses if they are not flagged for exclusion due to a protocol deviation relevant to the evaluation of PK (to be decided no later than in the Report Planning Meeting) or due to PK non-evaluability (as revealed during data analysis, based on the criteria specified below). Exclusion of a subject’s data will be documented in the CTR.

Relevant protocol deviations may be

- *Incorrect trial medication taken, i.e. the subject received at least one dose of trial medication the subject was not assigned to*
- *Incorrect dose of trial medication taken*

- *Use of restricted medications*

Plasma and urine (in the SRD part of the trial) concentrations and/or parameters of a subject will be considered as non-evaluable, if for example

- *The subject experienced emesis that occurred at or before two times median t_{max} of the respective treatment (Median t_{max} is to be determined excluding the subjects experiencing emesis),*
- *Missing samples/concentration data at important phases of PK disposition curve.*

In addition, plasma concentrations and/or parameters of a subject will be considered as non-evaluable in the BA part of the trial, if for example

- *The subject experiences emesis at any time during the labelled dosing interval.*
- *A predose concentration is $>5\% C_{max}$ value of that subject*

Plasma and urine (in the SRD part of the trial) concentration data and parameters of a subject which is flagged for exclusion will be reported with its individual values but will not be included in the statistical analyses. Descriptive and inferential statistics of PK parameters will be based on the PKS.

Table 6.3: 1 Subject sets analysed

Class of endpoint	Subject set		
	Treated set	PKS	ECGPCS
Primary endpoint and further safety assessments (incl. ECG)	X		
Analyses of PK endpoints		X	
Analyses of PD/biomarker endpoints	X		
ECG exposure response analysis			X
Demographic/baseline parameters	X		
Important protocol deviations	X		
Disposition	X		
Exposure	X		

6.5 POOLING OF CENTRES

This section is not applicable, because the study was performed in only one centre.

6.6 HANDLING OF MISSING DATA AND OUTLIERS

Handling of missing data and outliers will be performed as described in the CTP, Section 7.5.

The only exceptions where imputation might be necessary for safety evaluation are AE dates. Missing or incomplete AE dates are imputed according to BI standards (see BI-KMED-BDS-HTG-0035) (4).

Missing data and outliers of PK data are handled according to BI standards (see BI-KMED-TMCP-MAN-0012 (5) and BI-KMED-TMCP-MAN-0014 (6)).

If single cardiac cycles of an ECG (out of the generally four) are missing, the arithmetic mean for this single ECG will be computed with the reduced (1, 2 or 3) number of cardiac cycles.

If replicate ECG recordings are missing, the arithmetic means per time point will be computed with the reduced number (1 or 2) of recordings.

For the classification of the on-treatment QTc/QT intervals into ‘no new onset’ / ‘new onset’ categories, the handling of missing value is described in Appendix [Section 10.1.3](#).

For subjects on active drug (e.g. post dose time points), missing plasma concentration values with ‘BLQ’ in the comment field will be replaced by $\frac{1}{2}$ LLOQ for the exposure-response analysis.

For placebo subjects, the missing plasma concentration values will be replaced by 0 for the exposure-response analyses.

For PK analysis, missing data and outliers of PK data are handled according to BI standards [\(6\)](#) and [\(9\)](#).

6.7 BASELINE, TIME WINDOWS AND CALCULATED VISITS

SRD part: The baseline value is defined as the last measurement before first administration of trial medication (BI 474121 or Placebo).

BA part: The baseline value is defined as the last measurement before administration of trial medication in each treatment period (e.g. ptm -2:00).

For laboratory analysis, the last value on treatment will be defined as the last value during corresponding treatment period (usually 96:00h in first and second treatment period).

Adherence to time windows will be checked via the consistency check listings at the RPM.

Unscheduled measurements of laboratory data and vital signs data will be assumed to be repeat measurements of the most recent scheduled measurement (e.g. for follow-up or confirmation of a particular value). Therefore, unscheduled measurements will be assigned to the planned time point of the previous scheduled measurement.

There will be a centralised evaluation of the 12-lead ECG recordings of the SRD part at the time points and for the ECG recordings specified in [Table 6.7: 1](#) below:

Table 6.7: 1 Time schedule of 12-lead ECG recordings (SRD part)

Visit	Day	Planned time [hh:mm] (relative to drug administration)	Study phase	Central evaluation
1	-21 --1		Screening	NA
2	1	-01:00	Baseline	first ECG of each of the 3 triplicate baselines
		-00:45		
		-00:30		
		00:30		
		01:00		
		01:30		
		02:00		
		03:00		
		04:00		
		06:00		
		08:00		
		12:00		
	2	24:00		
		34:00		
	3	48:00	On-treatment	first single ECG of the triplicate
	4	72:00		
	5	96:00		
5	8-15		End-of-study examination	NA

At Screening and End-of-study examination ECG recordings are performed as single ECGs and will not be transferred to central ECG lab. Three triplicate ECGs will be recorded as the baseline before the first drug administration, but only the first ECG of each of the 3 baseline triplicates will be transferred to the database. At all other time points, 1 triplicate ECG will be recorded, but only the first single ECG of the triplicate will be transferred to the database. The baseline value of an ECG variable is defined as the mean of the ECG variable values prior to drug administration.

For the exposure-response analyses, acceptable maximum time deviations between ECG recordings and plasma concentration sampling are necessary (see the definition of the ECGPCS in [Section 6.3](#)). These are defined as 10 min until 1 hour after dosing, 20 min from including 1.5 hours up to 12 hours after dosing and as 1 h for time points including 12 hours after dosing and later. Pairs with time deviations exceeding those specified above will be excluded from exposure-response analyses. When the sampling time of the blood sample or the ECG recording is not available, the pair will also be excluded.

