All ECGs will be recorded for a 10 sec duration after subjects have rested for at least 5 min in a supine position. ECG recording will always precede all other study procedures scheduled for the same time (except for blood drawing from an intravenous cannula that is already in place) to avoid compromising ECG quality.

Proprietary confidential information © 2020 Boehringer Ingelheim International GmbH or one or more of its affiliated companies

ECGs will be recorded as single ECGs or as triplicate ECGs (i.e. three single ECGs recorded within 180 sec) as indicated in the [Flow Charts](#).

ECGs may be repeated for quality reasons for instance due to alternating current artefacts, muscle movements, or electrode dislocation. For repetition within triplicate ECGs the time window of 180 sec applies as well. The repeat ECGs are assigned to the respective scheduled time point.

Additional (unscheduled) ECGs may be recorded for safety reasons. These ECGs are assigned to the prior scheduled time point in the sponsor's database.

Storing

All ECGs will be stored electronically on the Muse Cardiology Information System (█
█).

ECGs recorded during visit 2 of the SRD part will be evaluated by a central lab, while ECG recordings during the BA part will be only evaluated locally.

Data transfer

In the SRD part of the trial, for time points specified in the Flow Chart, ECGs will be transferred electronically to the central ECG lab █ for evaluation and/or storage except for ECGs from screening and EoTrial visits which will not be transferred.

In case of repeat ECGs due to quality reasons, only the repeated ECG recordings will be transferred to the central ECG lab, whereas the initially recorded ECGs will be discarded. Unscheduled ECGs (for safety reasons) will be transferred to the central ECG lab but will not be included into the statistical analysis of interval lengths.

Data transfer from the central ECG lab to the sponsor is described in the ECG data transfer agreement (see TMF).

Evaluation

a) Central ECG lab

Central ECG lab evaluation will be performed post-study for the first of three replicate ECGs per time point on Days 1 to Day 3 and for the single ECGs on Day 4 and 5. This will include the determination of cardiac QRS-axis as assessed by the ECG machine's algorithm as well as the intervals RR, PR, QRS and QT measured semi-automatically.

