7.3.4 Safety analyses

Safety will be assessed as defined by the endpoints listed in Section [2.1.2](#) and [2.2.2](#) based on the treated set (TS). Safety analyses will be descriptive in nature and will be based on BI standards.

For all analyses the treatment actually administered (= treatment at onset) to the subject will be used (any deviations from the randomised treatment will be discussed in the minutes of the Report Planning Meeting).

Treatments will be compared in a descriptive way. The placebo group in the safety evaluation will consist of all subjects treated with placebo, regardless of the dose group in which they were treated. The test treatment groups will be compared to the placebo group in a descriptive

Proprietary confidential information © 2020 Boehringer Ingelheim International GmbH or one or more of its affiliated companies

way. Tabulations of frequencies/proportions will be used for the evaluation of categorical (qualitative) data, and tabulations of descriptive statistics will be used to analyse continuous (quantitative) data.

Measurements (such as ECGs, vital signs, or laboratory parameters) or AEs will be assigned to treatments (see Section 4.1) based on the actual treatment at the planned time of the measurement or on the recorded time of AE onset (concept of treatment-emergent AEs). Therefore, measurements planned or AEs recorded prior to intake of trial medication will be assigned to the screening period, those between the trial medication intake and end of REP (see Section 1.2.6) or next intake of study medication (BA part) will be assigned to the treatment period. Events occurring after the REP but prior to trial termination date will be assigned to 'follow-up'. These assignments including the corresponding time intervals will be defined in detail in the TSAP. Note that AEs occurring after the last per protocol contact but entered before database lock will be reported to Pharmacovigilance only and will not be captured in the trial database.

Additionally, further treatment intervals (called analysing treatments) may be defined in the TSAP in order to provide summary statistics for other than above periods, such as combined treatments, on-treatment totals, or periods without treatment effects (such as screening and post-study intervals).

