7.8.2 Laboratory data

The analyses of laboratory data will be descriptive in nature and will be based on BI standards [BI-KMED-BDS-HTG-0042] ([13](#)).

Laboratory data will be analysed qualitatively via comparison of laboratory data to their reference ranges. Values outside the reference range as well as values defined as possibly clinically significant will be flagged in the data listings.

Clinically relevant findings in laboratory data will be reported as baseline conditions (at screening) or as AEs (during the trial) if judged clinically relevant by the investigator, and will be analysed as such.

It is the investigator's responsibility to decide whether a lab value is clinically significantly abnormal or not (at the RPM at the latest).

Descriptive statistics of laboratory data including change from baseline will be calculated by planned time point based on the worst value of the subject at that planned time point (or assigned to that planned time point).

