7.8.3 Vital signs

For vital signs (blood pressure and pulse rate), descriptive statistics including change from baseline will be calculated by dose group and by planned time point based on the last value of the subject at that planned time point (or assigned to that planned time point). In the listing the difference from baseline will also be displayed.

Descriptive statistics over time will also be provided for the orthostatic test results (SRD part only) to enable checking of orthostatic hypotension occurrence. Subjects should have spent at least 5 min in the supine position before blood pressure and pulse rate will be measured the first time. Further 2 measurements will be performed immediately after standing up and after 3 min in a standing position. An orthostatic hypotension is defined as a decline in systolic blood pressure of ≥ 20 mmHg or a decline in diastolic blood pressure of ≥ 10 mmHg within the first three minutes after standing up.

Clinically relevant findings in vital signs will be reported as AEs.

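### SAP 6.7 maps unscheduled laboratory and vital-sign readings back across the dose, so early post-dose readings are tabulated as pre-dose

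*SAP*

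**What the plan says.** SAP 6.7 treats any extra reading as a re-check: "Unscheduled measurements of laboratory data and vital signs data will be assumed to be repeat measurements of the most recent scheduled measurement". It then gives the consequence: "Therefore, unscheduled measurements will be assigned to the planned time point of the previous scheduled measurement". Neither sentence mentions dosing.

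The summary rules use the mapped time point. Laboratory statistics (SAP 7.8.2) are "based on the worst value of the subject at that planned time point (or assigned to that planned time point"). Vital-sign statistics (SAP 7.8.3) are "based on the last value of the subject at that planned time point (or assigned to that planned time point").

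Protocol 7.3.4 says that measurements "will be assigned to treatments (see Section 4.1) based on the actual treatment at the planned time of the measurement". Those planned before intake go to the screening period. Those planned between intake and the end of the residual effect period, or the next intake in the BA part, go to the treatment period. It leaves the details to the SAP, but SAP 6.1 defines study phases only for adverse events.

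For the BA part, SAP 6.7 says of baseline: "The baseline value is defined as the last measurement before administration of trial medication in each treatment period", with -2:00 as its example.

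**The concern.** Treating an unscheduled reading as a repeat makes sense when it confirms the value just before it. It does not make sense when a dose lies between the two, because the later reading is then the first observation on drug.

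An unscheduled reading soon after dosing may well be prompted by a symptom, so it can be one of the more informative values for acute tolerability. Protocol 1.4.3 names haemodynamic effects and early detection of skeletal muscle injury as things to watch, and vital signs and set C laboratory tests serve those aims. As the rule stands, such a reading is missing from the post-dose rows and alters the pre-dose row. With 6 active subjects per SRD dose group and 12 in the BA part, one value can visibly change a row.

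**Working it through.** The plan gives no figure of its own to reproduce. The check applies the mapping rule to the schedule.

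**Step 1. Inputs.** Scheduled times come from the SRD and BA flow charts, and laboratory set contents from protocol Table 5.2.4: 1. Some flow-chart columns are broken in the available text. SRD pre-dose vital signs and set C laboratory were read as -1:00, and the last SRD pre-dose laboratory outside set C as about -72:00 (set E).

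**Step 2. Rule.** Mapped time = latest scheduled time at or before the actual time. The exposed window runs from dosing to the first scheduled post-dose assessment.

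| Data | Last pre-dose time | First post-dose time | Window mapped to pre-dose |
|---|---|---|---|
| SRD vital signs | -1:00 | 0:30 | 0–0.5 h |
| BA vital signs, each period | -2:00 | 4:00 | 0–4 h |
| Set C laboratory, SRD | -1:00 | 6:00 | 0–6 h |
| Set C laboratory, BA | -2:00 | 6:00 | 0–6 h |
| Other laboratory, SRD, matched by parameter | about -72:00 | 24:00 | 0–24 h |
| Other laboratory, BA, matched by parameter | -2:00 | 24:00 | 0–24 h |

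If laboratory values are matched by sampling occasion instead of by parameter, the last two windows shrink to 0–6 h. The SAP does not say which applies.

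**Step 3. Which value fills the row.** For vital signs the last value assigned to the time point is used, so a post-dose reading mapped there displaces the true pre-dose value. For laboratory data the worst value is used, so displacement occurs only when the post-dose value is worse.

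**Step 4. Treatment label.** The mapped planned time precedes intake, so protocol 7.3.4 does not give the reading on-treatment status for the dose just taken.

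**Step 5. Size, on assumed values only.**
- BA part, n = 12, assumed pre-dose systolic pressure 120 mmHg, one unscheduled 85 mmHg at 2 h: pre-dose mean = (11 × 120 + 85)/12 = 117.1 mmHg. The pre-dose row then has a value of 85 that no post-dose row shows.
- SRD dose group, n = 6 on active drug, assumed CK 150 U/L, one unscheduled 1000 U/L at 3 h: pre-dose mean = (5 × 150 + 1000)/6 = 291.7 U/L.

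These figures are illustrations, not forecasts. The documents give no expected frequency of unscheduled readings.

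**Step 6. Which BA period receives the reading.** Each period has its own -2:00 assessment, so a reading soon after the Period 2 or 3 dose maps to that same period's -2:00. On the phase rule in protocol 7.3.4, with a residual effect period of 7 × 24 = 168 h and a washout of at least 168 h:
- dose interval 168 h: -2:00 is 168 − 2 = 166 h after the previous dose, inside the period;
- dose interval 170 h: 170 − 2 = 168 h, on the boundary;
- dose interval 171 h: 171 − 2 = 169 h, outside it.

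**The case against.** The strongest reply is that little is lost. Laboratory and vital-sign changes that the investigator judges clinically relevant are recorded as adverse events, and these are assigned by recorded onset. All individual values are listed, and out-of-range and possibly clinically significant laboratory values are flagged. Baseline is the last measurement before administration, so on a clock-time reading a post-dose value cannot become baseline and later changes from baseline are not distorted. In the SRD part a misplaced value still stays in its own dose group. Dose escalation rests on safety reviews of the available data, not on these tables. All of this stands and limits the harm, but none of it moves the reading to the correct row.

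It can also be said that the technical analysis data set plan cited in SAP 6.1, or the sponsor's laboratory standard, may contain a dosing condition. Neither is available, and such a condition would contradict SAP 6.7 as written.

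Two stronger readings are tempting, and the documents do not support them:
- A reader might infer that SAP 6.7 credits the reading to the previous BA treatment. It does not. SAP 6.7 uses -2:00 as the new period's baseline and places the last on-treatment laboratory value of Periods 1 and 2 usually at 96:00. Only the planned-time wording in protocol 7.3.4 could give the previous treatment, and only at dose intervals of 170 h or less. The scheduled -2:00 value would then be labelled the same way, so the cause is not the rule for unscheduled readings.
- A reader might extend the point to ECGs, since protocol 5.2.5.1 says "These ECGs are assigned to the prior scheduled time point". The same section excludes unscheduled ECGs from the statistical analysis of interval lengths, so no interval summary changes.

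**Conclusion.** The point holds and is minor. Followed as written, SAP 6.7, 7.8.2 and 7.8.3 place an unscheduled laboratory or vital-sign reading taken early after dosing in the pre-dose row, and protocol 7.3.4 then does not class it as on-treatment. The gap is widest for BA vital signs (4 h) and laboratory data (6 h, or up to 24 h), and narrow for SRD vital signs (30 minutes).

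The effect is confined to descriptive laboratory and vital-sign summaries. The SRD primary endpoint (drug-related adverse events) and the PK endpoints are unaffected. It would go too far to infer a general bias of the safety comparison towards no effect, given the adverse-event route and the listings.

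This rests on the flow-chart times as read above, on baseline being taken by clock time, and on no unseen document overriding the SAP. The practical size depends on how many unscheduled readings fall in these windows, which the documents do not say.

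**What to change.** Amend SAP 6.7 so that an unscheduled laboratory or vital-sign value maps to the previous scheduled time point only if no trial medication was given between that time point and the reading. Otherwise show it at the first scheduled post-dose time point, or in a separate row labelled as unscheduled, on treatment. Set study phase, treatment and baseline eligibility for unscheduled values by actual time relative to dosing. State whether laboratory matching is by parameter or by sampling occasion.

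Separately, align protocol 7.3.4 with SAP 6.7 so that the BA -2:00 value belongs to the new period even when the dose interval is 170 h or less.

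The cost is a few sentences in the SAP, one condition in the derivation program and the alignment of 7.3.4. No new data are needed: protocol 6.1 already has exact times documented for measurements outside their permitted windows.
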